9.7.2.1 General Considerations

Statistical analyses will be descriptive only. No statistical inference or imputations of missing data are planned.

Subject demographics and baseline characteristics will be summarized. Summary statistics for continuous variables will include the number of subjects, mean, median, standard deviation or standard error, minimum, and maximum. For categorical variables, the frequency and percentage will be reported.

At the individual subject level, collection of data may be both retrospective and prospective, or prospective only. This depends on whether the subject enrolled some time after initiation of Repatha® (in which case their follow-up data is captured partially retrospectively) or whether the subject enrolled upon initiation of Repatha® (in which case the subject's follow-up data is collected prospectively in its entirety). Data obtained from subjects whose follow-up data are in part collected retrospectively may be reported separately from those with data collected fully prospectively to assess the potential for systematic differences between these subject groups.

9.7.2.2 Missing or Incomplete Data and Lost to Follow-up

The primary outcome measures are commonly recorded and/or already known to the treating physician. Incomplete information is not expected in this regard.

To evaluate the secondary objectives, the study intends to capture variables expected to be recorded as part of routine follow-up in this cardiovascular high risk population.

Measurement of laboratory variables (eg LDL-C) may be infrequent, however Investigators are expected to be interested in checking this parameter more closely following administration of a novel therapeutic, hence it is expected that LDL-C measurements will be taken during the follow-up period of all subjects enrolled in the study. Likewise, accuracy in reporting use of Repatha® and concomitant LMTs can be expected in this situation.

Where data appears to be incomplete in the study database, the study monitor will encourage sites to provide as much information as possible, from patient notes.

For relevant calendar dates that are partially complete, where possible an algorithm will be utilised to impute eg the missing day. Details of this algorithm are described in the statistical analysis plan. There will be no imputation for any other missing data fields.

Based upon data from the long-term Phase III studies Descartes and Osler ([Blom et al 2014](#), [Sabatine et al 2015](#)), a lost-to-follow-up rate of around 10% might be expected in this study. However, the low dropout rate in long-term interventional Phase III studies of evolocumab indicates subjects' willingness to continue on therapy. The incidence of discontinuation may be expected to be lower in an observational study, which does not carry the burden of additional study visits and invasive laboratory investigations.

Subjects lost to follow up will not be replaced.

9.7.2.3 Descriptive Analysis

9.7.2.3.1 Description of Study Enrolment

Eligible patients at each study site will be invited by the Investigator to provide informed consent to be enrolled into the study.

9.7.2.3.2 Description of Subject/Patient Characteristics

Subjects are adult patients who have been prescribed Repatha® as part of routine treatment at centres in Europe, and who provide informed consent to participate in the study.

Inclusion criteria have been written to be as inclusive as possible of the population initiated on Repatha® in the post-launch period.

9.7.2.4 Analysis of the Primary, Secondary and Exploratory Endpoints

9.7.2.4.1 Analysis of Primary Endpoints

Summaries displaying frequency and percentage, with 95% confidence intervals will be presented for FH status, CV history and diabetic status at the time of initiation of Repatha®.

Summary statistics displaying the number of subjects, mean, median, standard deviation or standard error, 25th percentile (Q1), 75th percentile (Q3), minimum, and maximum will be presented for LDL-C and HbA1C levels) at the time of initiation of Repatha®.

9.7.2.4.2 Analysis of Secondary Endpoints

Summaries displaying frequency and percentage, with 95% confidence intervals will be presented for gender, country, use of Repatha® (at initiation of Repatha® and over time), lipid-modifying therapies (at initiation of Repatha® and over time), medication adherence, medication persistence, incidence of hospitalization (including reason for admittance/final diagnosis), and incidence of physician visits.

Summary statistics displaying the number of subjects, mean, median, standard deviation or standard error, 25th percentile (Q1), 75th percentile (Q3), minimum, and maximum will be presented for age (at initiation of Repatha®) and LDL-C over time.

9.7.2.4.3 Exploratory Endpoint

A Summary displaying frequency and percentage, with 95% confidence intervals will be presented for incidence of LDL-C < 50 mg/dL (< 1.3 mmol/L)

9.7.2.5 Sensitivity Analysis

The primary analysis, summarizing data for each country separately, will include all data pooled, regardless of whether the data was collected retrospectively or prospectively. Sensitivity analyses will be performed subsetting the data according to the amount of retrospective data capture post-Repatha® initiation, to assess any differences in data completion for subjects with a greater or smaller duration of retrospective data capture.

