- Enrolment occurs only after initiation of Repatha® at physician discretion, independent of study protocol
- Where enrolment into study occurs after Repatha® initiation; all relevant follow-up data between Repatha® initiation and prior to study enrolment will be captured in a retrospective manner
- Calendar time for enrolment period at a country level is dependent on launch in each country; the enrolment period for the study on the whole is anticipated to span from Q1 2016 to Q4 2018
- Follow-up at the individual subject level continues for up to 30 months from start of Repatha® treatment irrespective of whether subject continues to receive Repatha®

1. Table of Contents

Summary Table of Study Protocol	1
Study Design Schema.....	5
1. Table of Contents.....	6
2. List of Abbreviations.....	9
3. Responsible Parties	10
4. Abstract.....	10
5. Amendments and Updates.....	14
6. Milestones	15
7. Rationale and Background.....	15
7.1 Diseases and Therapeutic Area	15
7.2 Rationale	16
7.3 Statistical Inference (Hypothesis).....	17
8. Research Question and Objectives.....	17
8.1 Primary Objective	17
8.2 Secondary Objectives.....	17
8.3 Exploratory Objective	17
9. Research Methods	17
9.1 Study Design	17
9.2 Setting and Study Population	18
9.2.1 Study Period.....	18
9.2.2 Selection and Number of Sites.....	18
9.2.3 Subject Eligibility.....	18
9.2.3.1 Inclusion Criteria	18
9.2.3.2 Exclusion Criteria	18
9.2.4 Matching.....	19
9.2.5 Baseline Period	19
9.2.6 Study Follow-up.....	19
9.3 Variables.....	19
9.3.1 Exposure Assessment.....	19
9.3.2 Outcome Assessment	19
9.3.2.1 Primary Outcome	19
9.3.2.2 Secondary Outcomes	20
9.3.2.3 Exploratory Outcome	21
9.3.3 Covariate Assessment.....	21
9.3.4 Validity and Reliability.....	21
9.4 Data Sources.....	21

9.5	Study Size	21
9.6	Data Management	23
9.6.1	Obtaining Data Files	24
9.6.2	Linking Data Files	24
9.6.3	Review and Verification of Data Quality	24
9.7	Data Analysis.....	24
9.7.1	Planned Analyses.....	24
9.7.1.1	Interim Analyses	24
9.7.1.2	Primary Analysis	24
9.7.2	Planned Method of Analysis	24
9.7.2.1	General Considerations	25
9.7.2.2	Missing or Incomplete Data and Lost to Follow-up	25
9.7.2.3	Descriptive Analysis.....	26
9.7.2.4	Analysis of the Primary, Secondary and Exploratory Endpoints.....	27
9.7.2.5	Sensitivity Analysis	27
9.7.3	Analysis of Safety Endpoint(s)/Outcome(s).....	28
9.8	Quality Control.....	28
9.9	Limitations of the Research Methods	29
9.9.1	Internal Validity of Study Design.....	29

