9.2.3 Subject Eligibility

9.2.3.1 Inclusion Criteria

All inclusion criteria need to be met, as follows:

- Adults (\geq 18 years)
- Provided informed consent if applicable according to local requirements
- Initiated on Repatha® at physician's discretion, after 1st August 2015
- Received at least one dose of Repatha®

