9.9.1.2 Selection Bias

At the site level, to avoid enrolment bias via selective invitation of a particular subject profile to participate in the study, all eligible patients will be invited to enrol in chronological order of attending the clinic, until the local enrolment cap has been reached. This also minimises selection of study subjects based on patient progress through the 30 month follow-up period.

It is possible that there could be differential follow-up over the 30 month post-initiation if subjects with certain characteristics, eg, those with less elevated LDL-C, were more likely to drop out than others. To explore this, an analysis set of study completers will be defined, and the primary outcome measure for that analysis set will be presented along with the primary analysis for the full analysis set (ie, all eligible subjects enrolled).

Patients who have received one dose of Repatha® only are also eligible to participate in the study, reducing the potential for selection bias to only those patients who remain on therapy for sufficient time to enrol into the study.

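### Enrolment can trail initiation by up to about 41 months and runs through clinic attendance, so persistence counted from first dose is open to survivor selection that the 9.7.2.5 sensitivity analysis is not aimed at

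*Protocol*

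**What the plan says.** The Study Design Schema states "Enrolment occurs only after initiation of Repatha® at physician discretion, independent of study protocol", and that "all relevant follow-up data between Repatha® initiation and prior to study enrolment will be captured in a retrospective manner". The inclusion criteria (9.2.3.1) require only "Initiated on Repatha® at physician's discretion, after 1st August 2015". Neither these nor the exclusion criteria limit the time from initiation to enrolment. The schema adds that "the enrolment period for the study on the whole is anticipated to span from Q1 2016 to Q4 2018".

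On recruitment, 9.9.1.2 says "all eligible patients will be invited to enrol in chronological order of attending the clinic", up to a local cap. It presents the eligibility of one-dose patients as "reducing the potential for selection bias to only those patients who remain on therapy for sufficient time to enrol into the study".

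Follow-up runs 30 months from first dose (9.2.6), and persistence is defined as the subject's time on therapy (List of Abbreviations). Persistence and hospitalisation are summarised as percentages with 95% confidence intervals (9.7.2.4.2). All data are pooled, whether retrospective or prospective (9.7.2.5).

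Three provisions touch on the resulting selection:

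- 9.7.2.5 subsets by amount of retrospective capture, "to assess any differences in data completion for subjects with a greater or smaller duration of retrospective data capture".
- 9.7.2.1 says "collection of data may be both retrospective and prospective, or prospective only", and that the two groups may be reported separately to look for systematic differences.
- 9.9.1.2 defines a completers set, for the primary outcome only, to explore differential drop-out during follow-up.

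**The concern.** A subject contributes time from first dose, yet enters the study only by still being reachable at a later clinic visit. Time before enrolment is therefore partly guaranteed: someone who stopped after two months and no longer attends is unlikely to be in the data, while someone still on treatment is. This is left truncation, and it pushes persistence upward. It may also leave out admissions that were fatal or that ended attendance. LDL-C over time describes the same selected group.

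One-dose eligibility removes a formal exclusion, but a one-dose patient must still come to the clinic to be invited. The protocol already commits to the useful subsets, by retrospective duration, but directs them at data completion and not at the outcomes exposed to the selection. Sections 4 and 7.2 say the data are meant to support continuation or reassessment of access, so a bias that flatters persistence matters to the intended reader.

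**Working it through.** **1. The plan's own precision figure.** Section 9.5 gives a half-width of about 8% for 130 subjects and a proportion of 35%: 1.96 × √(0.35 × 0.65 / 130) = 8.2%. It reproduces. For a proportion of 80% the same formula gives 1.96 × √(0.80 × 0.20 / 130) = 6.9 points. These figures cover sampling error only.

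**2. The lag the dates allow.**

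- Maximum: 1 August 2015 (9.2.3.1) to the end of Q4 2018 (schema) is about 41 months.
- Wholly retrospective follow-up: 1 August 2015 plus 30 months is 1 February 2018, inside the enrolment window. A patient who started then and enrolled later in 2018 would have all 30 months before enrolment. Section 9.7.2.1 lists only mixed or fully prospective collection.
- Minimum for the earliest initiators: about 5 months to the start of Q1 2016, or about 8 months to the start of data collection in April 2016 (Section 6).

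**3. Illustrative size.** The protocol gives no persistence, lag distribution or enrolment probability, so all three are assumptions here. Take constant-hazard discontinuation with 12-month persistence 0.80, lag uniform over 0-12 months and independent of discontinuation, and probability q that a patient who stopped before the lag is enrolled, relative to one who did not.

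- Average share still on therapy at enrolment: (1 − 0.80) / (−ln 0.80) = 0.20 / 0.2231 = 0.896.
- Pooled 12-month persistence: 0.80 / (0.896 + 0.104q).

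For lag over 0-24 months, the share enrolled is 0.807 + 0.193q, and the share enrolled and on therapy at 12 months is 0.759 + 0.041q.

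| q | Lag 0-12 months | Lag 0-24 months |
|---|---|---|
| 0.75 | 82.1% | 83.0% |
| 0.50 | 84.4% | 86.3% |
| 0.25 | 86.7% | 89.9% |

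With a true value of 90% and lag over 0-12 months, the expression becomes 0.90 / (0.949 + 0.051q), giving 91.2% (q = 0.75) to 93.6% (q = 0.25). With no lag, or with q = 1, the bias is zero.

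Against the 6.9-point half-width at 80%, the overstatement of 2 to 10 points runs from minor to larger than the sampling error.

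**4. How a delayed-entry estimate behaves.** Under the same model it centres on 80%, because lag was made independent of discontinuation. Simulated at 130 subjects, about 11 are at risk at month 1 for lags of 0-12 months and about 6 for 0-24 months. Its standard deviation is about 7 to 11 points, against about 3 for the pooled estimate. Its root mean squared error is larger in five of the six scenarios and about equal in the sixth (lag 0-24 months, q = 0.25). At the planned total of 2000 subjects with q = 0.50 the order reverses: root mean squared error is about 2.0 against 4.4 points (lag 0-12) and 2.8 against 6.3 points (lag 0-24).

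**The case against.** The strongest reply has several parts.

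- **The protocol is not silent on selection.** It invites patients in order of attendance, admits one-dose patients, and allows separate reporting of partly retrospective and fully prospective subjects. This is right, and 9.9.1.2 claims to reduce the bias, not to remove it. But the separate reporting is optional and names no endpoint, and none of these measures reaches patients who have left the clinic.
- **The estimator belongs in the statistical analysis plan.** That plan is not shown and may go further. The purpose of the retrospective-duration subsets, however, is fixed in the protocol and can be judged there.
- **The sizes are assumed.** They are. A 41-month gap is also an extreme, needing a late-opening site or a long absence from the clinic. The illustration shows what is possible, not what is expected.
- **Hospitalisation is less clear than persistence.** Non-fatal admissions before enrolment are captured from charts, and sicker patients may attend and enrol sooner. The net direction is not established.
- **Delayed entry is imprecise at country level.** Step 4 of the working confirms it.

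Two stronger readings are tempting. A reader might infer that death rates from initiation are understated. Death ends follow-up and is collected as safety information, but it is in no outcome list (9.3.2.1 to 9.3.2.3), and 9.7.3 plans only a summary of adverse drug reactions, so no such rate is to be estimated. A reader might also infer that comparisons between countries become artefacts. None is planned: results are descriptive by country, and 9.9.2 warns that populations may differ.

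**Conclusion.** The point holds for persistence, and more weakly for admissions that are fatal or end attendance. With no cap on the lag, recruitment through attendance, counting from first dose and pooling of all time, persistence is at risk of overstatement, and the committed sensitivity analysis looks at data completion instead. Under the assumptions shown, a true 80% at 12 months would appear as 82-87% for lags of 0-12 months and 83-90% for lags of 0-24 months. The actual size depends on each country's lag and on how many early stoppers still attend. Consent is needed only where local rules require it, so exclusion of patients who died before invitation will vary. The primary objective, characteristics at initiation, is touched only through who is selected. The change is worth making because it is cheap and uses subsets already planned.

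**What to change.** - **9.7.2.5:** apply the retrospective-duration subsets, including one of subjects enrolled at or shortly after initiation, to persistence, hospitalisation and LDL-C over time as well as data completion. Report the initiation-to-enrolment lag by country.
- **9.7.2.5:** add, on the pooled sample, a supplementary delayed-entry estimate of persistence (time since initiation as the time scale, at risk from enrolment), shown beside the all-data estimate. It should not replace country-level estimates.
- **9.7.2.1:** recognise that follow-up can be wholly retrospective.
- **9.9.1.2:** keep the one-dose sentence but qualify it, saying that patients who left the clinic or died before invitation remain under-represented.

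The cost is wording and programming. No new data collection is needed, since both enrolment and Repatha initiation are recorded in the eCRF (Appendix C). The downside of the delayed-entry estimate is few subjects at risk early and wide intervals. It also leaves out early stoppers who enrolled after stopping, and it relies on lag being unrelated to discontinuation.

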9.7.2.5.1 Subgroup Analysis

Subgroup analysis will be conducted to be supportive of the primary analysis of the primary, secondary and exploratory endpoints. The subgroup analysis will be the planned analysis stratified by country. In addition, a selection of outputs will be generated for subgroups defined based on their status at Repatha® initiation: FH status

(HeFH, HoFH, no); Diabetic status (Type I, Type II, no); CV History (yes, no); Baseline LDL-C (< median, ≥ median); Age (< 65 years, ≥ 65 years).

9.7.3 Analysis of Safety Endpoint(s)/Outcome(s)

No formal analysis of Safety data is planned for this study. ADRs will be summarised.

9.8 Quality Control

Source data verification will be performed at the study site, in accordance with Amgen SOPs.

The Investigator is to maintain a list of appropriately qualified persons to whom he/she has delegated study duties. All persons authorized to make entries and/or corrections on CRFs will be included on the Amgen Delegation of Authority Form.

Source documents are original documents, data, and records from which the subject's CRF data are obtained. These include but are not limited to hospital records, clinical and office charts, laboratory and pharmacy records, diaries, microfiches, radiographs, and correspondence.

The Investigator and study staff are responsible for maintaining a comprehensive and centralized filing system of all study-related (essential) documentation, suitable for inspection at any time by representatives from Amgen and/or applicable regulatory authorities.

Elements to include:

- Subject files containing completed CRF, informed consent forms, as applicable, and subject identification list
- Study files containing the protocol with all amendments, copies of pre-study documentation, and all correspondence to and from the IRB/IEC or other relevant ethical review board and Amgen

In addition, all original source documents supporting entries in the CRFs must be maintained and be readily available.

Retention of study documents will be governed by the contractual agreement with Amgen.

Amgen retains all data, programs and outputs generated for the study. At study close, data are uploaded from the Medidata Rave database and stored in accordance with Amgen SOPs. Statistical programming and outputs are locked in the analysis environment and no updates are permitted; standard programming procedures will apply.

9.9 Limitations of the Research Methods

9.9.1 Internal Validity of Study Design

9.9.1.1 Information Bias

For the primary objective, information bias is not anticipated to be applicable, as Investigators will be aware of the subjects' age and gender, and will have paid particular attention to their CV history as they have been referred for CV cause. It is possible that lipids may be measured more frequently in very high risk and/or sicker patients, which could influence the baseline LDL-C; to help prevent this, a maximum of two LDL-C values in the 6 months prior to initiation of Repatha® will be considered for inclusion in the baseline, and these will be the two most recent values prior to the initiation date.

For the secondary objectives, it is expected that Investigators will follow all subjects closely as: 1. they have been initiated on a novel therapeutic in the immediate post-launch period. LDL-C values and use of Repatha® and any concomitant medications will be significant markers of clinical care, and are likely to be assessed on an ongoing basis over the observation period. 2. Subjects are high risk patients in secondary care.

9.9.1.2 Selection Bias

At the site level, to avoid enrolment bias via selective invitation of a particular subject profile to participate in the study, all eligible patients will be invited to enrol in chronological order of attending the clinic, until the local enrolment cap has been reached. This also minimises selection of study subjects based on patient progress through the 30 month follow-up period.

It is possible that there could be differential follow-up over the 30 month post-initiation if subjects with certain characteristics, eg, those with less elevated LDL-C, were more likely to drop out than others. To explore this, an analysis set of study completers will be defined, and the primary outcome measure for that analysis set will be presented along with the primary analysis for the full analysis set (ie, all eligible subjects enrolled).

Patients who have received one dose of Repatha® only are also eligible to participate in the study, reducing the potential for selection bias to only those patients who remain on therapy for sufficient time to enrol into the study.

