7.2 Rationale

EMA approval for Repatha® was granted on 17th July 2015. The data submitted in support of the filing were generated from an extensive interventional clinical trial programme in which selected populations were enrolled and managed according to strictly-defined protocols in a controlled setting. More recently, the 27,564 patient FOURIER trial which evaluated the effect of lowering LDL-C with evolocumab in subjects with established atherosclerotic disease reported a 20% relative risk reduction in major adverse cardiac events compared to those on optimized oral lipid lowering therapy ([Sabatine et al, 2017](#)). However, such data can not necessarily be generalised to routine clinical practice especially given the varying reimbursement rules and availability of the drug in participating countries, and at present there is little information describing Repatha® use in a real-world setting.

Across Europe, country health authorities grant local access approvals based on clinical trial data. As the next step, real world evidence describing product use in routine clinical practice are required, for continuation and/or reassessment of access. The design and objectives of this study address the anticipated requests being made by the health authorities. In particular, authorities require local real-world data on the patient population which is receiving Repatha®, including patient characteristics, dosing patterns and effectiveness in lowering LDL-C. The study will be conducted only in countries which require real world data to be collected in the post-launch setting and where it is allowed as per local regulations to study the use of a single treatment in clinical practice.

Data obtained from this study are intended to fulfil health authorities' requirements and to provide a robust source of published information for physicians.

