9.3.2.1 Primary Outcome

Clinical characteristics at time of initiation of Repatha® as assessed in relation to:

- FH status (diagnosed/not diagnosed)
- CV history (see [Appendix B](#) for a list of diagnoses/events)

- Diabetic status (diabetic/not diabetic; Type 1 or Type II; HbA1C measurement closest to initiation of Repatha®)
- Cholesterol values including total cholesterol, LDL-C, HDL-C, non-HDL-C, triglycerides (value(s) available in the 26-week baseline period)
- Demographics (age at initiation of Repatha®, gender, country)
- Cardiovascular risk factors (body mass index (BMI), smoking status, chronic kidney disease, history of hypertension, vascular bed involvement (see also [Appendix B](#)))
- History of statin intolerance (y,n)
- Dose, dose frequency, commencement date of Repatha® administration
- Type, dose, dose frequency, commencement and discontinuation dates of other LMT administration including apheresis
- Dates and reason for hospital admittance/final diagnosis
- Dates of physician visits and reason for attendance

Of note, LMT use (including apheresis) over the 6 months prior to initiation of Repatha® will be summarised and the regimen in place at the time of Repatha® initiation will be regarded as the baseline.

In addition, LDL-C and other relevant lipid panel measurements and HbA1C as assessed within 6 months prior to initiation of Repatha® (or the mean of the two most recent LDL-C measurements, if there is more than one) will be regarded as the respective baseline values.

All CV history and diabetic status will be reported as baseline data

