9.7.1.2 Primary Analysis

The summaries of FH status, CV history and diabetic status and the summary statistics of LDL-C will be presented for the time of initiation of Repatha®.

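### The dropout check in 9.9.1.2 sets baseline data for completers beside a set that contains them, and does not look at LDL-C over time

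*Protocol*

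**What the plan says.** Protocol 9.9.1.2 names the risk: "It is possible that there could be differential follow-up over the 30 month post-initiation if subjects with certain characteristics" were more likely to leave, the example being those whose LDL-C is less raised. Its response is to define a set of study completers and to state that "the primary outcome measure for that analysis set will be presented along with the primary analysis for the full analysis set". The full analysis set is explained as "ie, all eligible subjects enrolled", so every completer belongs to it.

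The primary outcome is a baseline one. Section 9.3.2.1 defines it as "Clinical characteristics at time of initiation of Repatha", and under 9.7.1.2 "the summary statistics of LDL-C will be presented for the time of initiation of Repatha".

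LDL-C over time is a secondary objective (8.2) and a secondary outcome (9.3.2.2). Section 9.7.2 takes each subject's mean within 3-month or 6-month windows and summarises those means; 9.7.2.4.2 says that the usual summary statistics "will be presented for age (at initiation of Repatha®) and LDL-C over time". On missing values, 9.7.2.1 says "No statistical inference or imputations of missing data are planned", and 9.7.2.2 makes an exception only for partial dates.

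The sensitivity analysis in 9.7.2.5 splits subjects by the amount of retrospective capture, and the subgroups in 9.7.2.5.1 are countries and baseline factors. Neither looks at subjects by follow-up status.

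Expected dropout is given in two ways: up to 10% per year over the 30 months (9.5), and about 10% with no time unit (9.7.2.2 and 9.9.3).

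**The concern.** Two features of the stated check limit what it can show.

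First, the two columns are nested. Completers beside everyone is not the same as completers beside those who left. The visible gap is only a fraction of the real one, and a reader who compares the columns by eye may conclude that dropout was unselective.

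Second, the outcome shown is fixed at initiation, so later dropout does not remove it. The result that dropout can distort is LDL-C over time. Subjects who leave stop contributing to later windows, and if they differ in LDL-C from those who stay, the window means move for that reason alone. Section 7.2 says that authorities want local data "including patient characteristics, dosing patterns and effectiveness in lowering LDL-C". A change in who is being measured could then be read as a change under treatment, and the stated check would not address it.

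**Working it through.** **Inputs.** N = 130 per country and 2000 in total, and SD 40 to 55 mg/dL with 50 used here (9.5). Dropout share d: 0.10 if the figure in 9.7.2.2 and 9.9.3 is read as a total; at 10% per year (9.5), 1 − 0.9^2.5 = 0.232 compounded, or 0.25 linear. The gap in baseline LDL-C between completers and non-completers is not given in the protocol; 10, 20 and 40 mg/dL are assumptions.

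**The plan's own figure.** Half-width of the 95% CI for mean LDL-C = 1.96 × 50 / √130 = 8.60 mg/dL, as in the table in 9.5.

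**What the display shows.** Let C, X and F be the means in completers, non-completers and the full set. Since F = (1 − d)C + dX, it follows that C − F = d(C − X).

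| Assumed gap C − X (mg/dL) | Shown, d = 0.10 | Shown, d = 0.232 | Shown, d = 0.25 |
|---|---|---|---|
| 10 | 1.0 | 2.3 | 2.5 |
| 20 | 2.0 | 4.6 | 5.0 |
| 40 | 4.0 | 9.3 | 10.0 |

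**Is information lost?** No. With N and mean reported for both sets, X = (N_F × F − N_C × C) / (N_F − N_C).

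**Is the direct contrast more precise?** Its half-width is 1.96 × 50 × √(1/n_C + 1/n_X):

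- One country, 23% dropout (100 and 30 subjects): 20.4 mg/dL. For SD 40 to 55 this scales to 16.3 to 22.4.
- One country, 10% dropout (117 and 13): 28.7 mg/dL.
- Pooled, 23% dropout (1537 and 463): 5.2 mg/dL.
- Pooled, 10% dropout (1800 and 200): 7.3 mg/dL.

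In one country with 30 non-completers, a true gap of 20 would be displayed as (30/130) × 20 = 4.6, and its half-width is (30/130) × 20.4 = 4.7. Both the displayed and the direct contrast have a ratio of gap to half-width of 0.98. Nesting shrinks the gap and its uncertainty alike.

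**Can a baseline check miss bias in LDL-C over time?** An illustrative simulation says yes. All its values are assumptions: baseline mean 150 and SD 50, follow-up mean 70 and SD 40, and about 23% dropout that becomes more likely as follow-up LDL-C rises. The completers' follow-up mean was off by about 5.3 mg/dL throughout. The baseline gap between the full set and completers was 0.0, 2.0 and 3.2 mg/dL when the correlation between baseline and follow-up was 0, 0.3 and 0.5. The direct baseline contrast was 0.1, 8.4 and 13.9 mg/dL. With no correlation, no baseline comparison of either kind reveals the problem; only follow-up values can.

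**The case against.** The best defence is that the check does what 9.9.1.2 asks. The question there is whether subjects with certain characteristics leave more often, and baseline characteristics of those who stay bear on it. That stands: the check is weak in display, not irrelevant.

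A reader might infer that nesting hides a gap beyond recovery, or that a displayed 2 to 5 mg/dL is undetectable because it lies inside the 8.6 mg/dL country half-width. Neither holds. The non-completer mean can be recovered exactly, and the full set's half-width is the wrong yardstick for a difference between nested sets. Setting a country half-width against the pooled 5.2 mg/dL would also mix levels.

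A reader might also infer that LDL-C over time will go unchecked, or that it will be biased. The documents support neither. The analysis plan is not shown and may add tables; the point is that the check the protocol itself states is aimed elsewhere. Nothing shows that dropout will be selective. Follow-up continues after Repatha is stopped (9.2.6), and chart review adds no study visits (9.7.2.2), so stopping treatment is not in itself dropout. The windows draw on one overlapping cohort and N is reported for each, so attrition will be visible, though not its pattern.

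Finally, the study is descriptive and its objective is to describe concentrations over time. That argues against requiring a model, but not against descriptive tables by completion status.

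**Conclusion.** The point holds in a limited form. The check in 9.9.1.2 displays between a tenth and a quarter of any baseline gap between completers and non-completers, depending on which of the protocol's dropout figures applies. This is an arithmetic identity and a matter of presentation; it costs neither information nor precision. The absolute sizes in the table rest on assumed gaps.

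The more important part needs no assumed number: the stated check does not examine LDL-C over time, although that is the result dropout can bias and one the authorities are said to want. How large such a bias would be cannot be derived from the protocol; the 5.3 mg/dL above only illustrates that a clean baseline table does not exclude it. The primary objective is unaffected.

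**What to change.** In 9.9.1.2, replace the stated comparison with three descriptive displays:

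- **(a)** Baseline characteristics, including LDL-C, for completers against non-completers, pooled over countries and stratified by or standardised for country. Section 9.9.2 expects populations to differ between countries, so a crude pooled contrast could confuse country mix with dropout.
- **(b)** LDL-C over time by completion status, with completers and non-completers shown separately and the non-completers' windows before dropout used.
- **(c)** For each window, within-subject change and percentage change from baseline in subjects with both values. This removes shifts due only to the baseline mix; it does not remove selection on response, which is why (b) is needed as well.

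A mixed model for repeated LDL-C would be an optional extra. It goes beyond a plan that is descriptive only, and the point does not depend on it.

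The cost is a few extra tables and no new data. Non-completer estimates within one country will be imprecise (half-width of the contrast about 20 to 29 mg/dL at N = 130 and SD 50), so the pooled display (about 5 to 7 mg/dL) should carry the interpretation.
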